Describe how potential subjects will be identified: Patient subjects will be identified based on the following inclusion/exclusion criteria using our best practice alert build in Epic:

- Age>18 Years
- Seen in internal medicine or cardiology clinic
- Left Ventricular Ejection Fraction ≤40%
- Yale Heart Failure Registry (NCT04237701)

Providers will be identified based on retrospective chart review by study investigators to determine the frequency with which they see eligible patients.

Describe how potential subjects are contacted. Eligible providers will be sent an email that includes the REDCap link which directs the providers to the electronic consent form. The email will be sent by one of the study team members. Should email contact be unsuccessful, we will attempt to consent providers via in-person signed consent, or via a waiver of documentation of consent via Epic inbasket messages or verbal telephone consent.

We will engage in pre-trial education (during the consent process) and periodic outreach to all participating clinicians, informing them of the nature of the study, the fact that it is a randomized trial, and describing the alert and evidence-based therapies for HFrEF. We will additionally inform them that limited data is being collected regarding provider behavior. However, we will also make it clear that this data will not be linked to individual clinicians or outcomes. All such data will only be analyzed in aggregate. Patient subjects will not be contacted, and we will be requesting a waiver of informed consent.

Who is recruiting potential subjects? For patients, this will be done electronically via the electronic health record. Patients will be identified if they are seen in outpatient general medicine or cardiology clinic and meet the inclusion and exclusion criteria stated above. Providers will be recruited and contacted by study coordinators and the principle investigator as described above.

4. Assessment of Current Health Provider Relationship for HIPAA Consideration:

Does the Investigator or any member of the research team have a direct existing clinical relationship with any potential subject?

- Yes, all subjects
- Yes, some of the subjects
- No

If yes, describe the nature of this relationship. Some members of the research team might have previously treated a subject. We do not foresee this impacting the care of any patient.

5. Request for waiver of HIPAA authorization: We are requesting HIPAA Waiver

Choose one:

- For entire study
- For recruitment/screening purposes only
- For inclusion of non-English speaking subject if short form is being used and there is no translated HIPAA research authorization form available on the University's HIPAA website at hipaa.yale.edu.

Describe why it would be impracticable to obtain the subject's authorization for use/disclosure of this data: Patient subjects will not be informed of their randomization status or participation in this trial as the trial could not be feasibly performed if subjects were told they were enrolled. All investigators will be blinded to treatment assignment until the end of the trial period. Care providers will, obviously, not be blinded to the intervention as they are receiving the alert and will consent to take part in the study.. We will engage in both pre-trial and periodic teaching and discussion with all consented care providers to inform clinicians about the nature of the study. A letter will be sent to the providers.

ii. If requesting a waiver of signed authorization, describe why it would be impracticable to obtain the subject's signed authorization for use/disclosure of this data: The study is being conducted under a waiver of informed consent. This research is minimal risk, as outlined above, and cannot be practicably performed in the absence of a waiver of informed consent (as patients randomized to the usual care arm would be required not to reveal their HF diagnosis to their providers). There is no infringement of rights or welfare of patients, as the alert has no direct effect on the patient, short of via the actions of their providers. Data abstracted from the medical record will be de-identified, as described in the confidentiality section above. Another defense against these risks is the alert language itself. Each alert calls attention to the fact that alerts are not issued for all patients with heart failure.

The investigator assures that the protected health information for which a Waiver of Authorization has been requested will not be reused or disclosed to any person or entity other than those listed in this application, except as required by law, for authorized oversight of this research study, or as specifically approved for use in another study by an IRB.

Researchers are reminded that unauthorized disclosures of PHI to individuals outside of the Yale HIPAA-Covered entity must be accounted for in the “accounting for disclosures log”, by subject name, purpose, date, recipients, and a description of information provided. Logs are to be forwarded to the Deputy HIPAA Privacy Officer.

6. Process of Consent/Accent: Eligible providers will be approached for consent in one of the methods described above. In cases where signed consent can occur, providers will be provided with a link that includes the REDCap link which directs the providers to the electronic consent form. The email will be sent by one of the study team members. The provider consent to participation by typing in their first and last name, include date/time of consent, and by signing the electronic consent. It will also have providers give their address, telephone number, and date of birth for purposes of payment through the OnCore system. Following that, the providers click on the “submit” button. Following that, the study team will then send a copy of the signed form to the provider along with a link to the REDCap survey.

Patient subjects will not be informed of their randomization status or participation in this trial as the trial could not be feasibly performed if subjects were told they were enrolled. Also,

there are no guideline-based specific recommendations based on a risk score assessment, or any other prognostic assessment for that matter. All investigators will be blinded to treatment assignment until the end of the trial period. Care providers will, obviously, not be blinded to the intervention as they are receiving the alert. We will engage in both pre-trial and periodic teaching and discussion with all consented care providers to inform clinicians about the nature of the study, evidence based guidelines and the specific factors that are being measured.

- 7. Evaluation of Subject(s) Capacity to Provide Informed Consent/Accent:** N/A (see above).
- 8. Non-English-Speaking Subjects:** Since the focus of this study is provider behavior, the language status of the subject would not matter.

Note* If more than 2 study participants are enrolled using a short form translated into the same language, then the full consent form should be translated into that language for use the next time a subject speaking that language is to be enrolled.

Several translated short form templates are available on the HRPP website (yale.edu/hrpp) and translated HIPAA Research Authorization Forms are available on the HIPAA website (hipaa.yale.edu). If the translation of the short form is not available on our website, then the translated short form needs to be submitted to the IRB office for approval via modification prior to enrolling the subject. ***Please review the guidance and presentation on use of the short form available on the HRPP website.***

If using a short form without a translated HIPAA Research Authorization Form, please request a HIPAA waiver in the section above.

- 9. Consent Waiver: In certain circumstances, the HIC may grant a waiver of signed consent, or a full waiver of consent, depending on the study.** If you will request either a waiver of consent, or a waiver of signed consent for this study, complete the appropriate section below.

Not Requesting any consent waivers

Requesting a waiver of signed consent: (for provider subjects only)

- Recruitment/Screening only** (*if for recruitment, the questions in the box below will apply to recruitment activities only*)
- Entire Study** (Note that an information sheet may be required.)

For a waiver of signed consent, address the following:

- Would the signed consent form be the only record linking the subject and the research? **YES**
 NO
- Does a breach of confidentiality constitute the principal risk to subjects? **YES** **NO**
OR
- Does the research pose greater than minimal risk? **YES** **NO**
- Does the research include any activities that would require signed consent in a non-research context? **YES** **NO**

Requesting a waiver of consent: (for patient subjects only) **Recruitment/Screening only (if for recruitment, the questions in the box below will apply to recruitment activities only)**

Entire Study

For a full waiver of consent, please address all of the following:

- Does the research pose greater than minimal risk to subjects?
 Yes If you answered yes, stop. A waiver cannot be granted.
 No
- Will the waiver adversely affect subjects' rights and welfare? **YES** **NO**
- **Why would the research be impracticable to conduct without the waiver?** The research proposed is of minimal risk to subjects. No procedures or tests are being performed. No additional studies are being requested. The sole intervention is an electronic alert that will be sent to relevant members of the subjects' clinical care team. The risk of the alert itself is minimal. Subjects will not be informed of their randomization status or participation in this trial as the trial could not be feasibly performed if subjects were told they were enrolled. All investigators will be blinded to treatment assignment until the end of the trial period. Care providers will, obviously, not be blinded to the intervention as they are receiving the alert. We will engage in both pre-trial and periodic teaching and discussion with all care providers (administered through short presentations at divisional conferences) to inform clinicians about the nature of the study, the fact that the same alerts do not fire for all patients with heart failure and to discuss specific factors that are being measured.
- **Where appropriate, how will pertinent information be returned to, or shared with subjects at a later date?** We expect that there will be considerable academic output that results from these efforts. This will be shared with the providers who participated in the study and any publication that result will be made available to the general public.

SECTION IV: PROTECTION OF RESEARCH SUBJECTS

Confidentiality & Security of Data:

1. **What protected health information (medical information along with the HIPAA identifiers) about subjects will be collected and used for the research?** Age, gender, date of birth and several categories of health information (provider encounters, notes, comorbidity, medication lists, problem lists, family history, allergies, laboratory findings, procedures, immunizations, vital signs, and medical record numbers) and relevant clinical

outcomes will be collected on subjects. This data will be deidentified. Individual provider data will not be collected.

- 2. How will the research data be collected, recorded and stored?** This data will initially be transferred to Clinical and Translational Research Accelerator (CTRA) to a data analyst associated with this project for cleaning. All YNHS patient data will then be shared using Yale ITS managed file transfer. This platform is a web-based application used to share data packages over the internet through a secure channel. When being shared, the data will be encrypted using https secure protocol. Access to this data will only be available to study personnel who are a part of the study team.
- 3. How will the digital data be stored?** CD DVD Flash Drive Portable Hard Drive Secured Server Laptop Computer Desktop Computer Other
- 4. What methods and procedures will be used to safeguard the confidentiality and security of the identifiable study data and the storage media indicated above during and after the subject's participation in the study?** All data used at Yale will be transferred over secure channels and encrypted during sending. Data will be stored on 3-lock compliant servers within Yale or on secure, Yale-issued IronKey devices. Only study personnel directly involved in data analysis with a need to access PHI will have access to these data.

All portable devices must contain encryption software, per University Policy 5100. If there is a technical reason a device cannot be encrypted please submit an exception request to the Information Security, Policy and Compliance Office by clicking on url <http://its.yale.edu/egrc> or email [contact]

- 5. What will be done with the data when the research is completed? Are there plans to destroy the identifiable data? If yes, describe how, by whom and when identifiers will be destroyed. If no, describe how the data and/or identifiers will be secured.** Data will be maintained on secure, encrypted servers at the Program of Applied Translational Research (PATR) after completion of the research study for a minimum of 5 years after publication of our findings in a peer-reviewed journal (in such case as there is a need to return to the original data source to validate a finding or respond to a question).
- 6. If appropriate, has a Certificate of Confidentiality been obtained?** Since the data obtained are from broad health characteristics from personal health records that do not target any particular sensitive research areas, a CoC has not been obtained.

SECTION V: POTENTIAL BENEFITS

Potential Benefits: Subjects in this study may benefit from their provider being given information about their prognosis. Regardless of the outcome for participants, the results of these studies may lead to significant societal benefit, as even a negative study would lead to less enthusiastic adoption of ineffective alerting. The risk/benefit ratio, given the minimal risk to study subjects, is more than acceptable in this series of studies.

SECTION VI: RESEARCH ALTERNATIVES AND ECONOMIC CONSIDERATIONS

1. **Alternatives:** The provider can dismiss the alert if they choose.

Payments for Participation (Economic Considerations): Patient subjects will not receive any payment. Provider subjects will receive payment in the form of a gift card for their completion of the pre- and post-trial surveys assessing their knowledge of guidelines and their overall experience with the alert. Providers will receive \$50 for completion of the pre-trial survey and \$200 for the completion of the post-trial survey. There is no payment directly connected to their experience with the alert itself (i.e. whether they accept or dismiss the alert, acknowledge or ignore the alert, etc.). All enrolled providers, regardless of randomization status, will partake in the study surveys and receive payment.

2. **Costs for Participation (Economic Considerations):** None.

3. **In Case of Injury:** Not applicable.

IMPORTANT REMINDERS

Will this study have a billable service? **No**

A billable service is defined as any service rendered to a study subject that, if he/she was not on a study, would normally generate a bill from either Yale-New Haven Hospital or Yale Medical Group to the patient or the patient's insurer. The service may or may not be performed by the research staff on your study but may be provided by professionals within either Yale-New Haven Hospital or Yale Medical Group (examples include x-rays, MRIs, CT scans, specimens sent to central labs, or specimens sent to pathology). Notes: 1. There is no distinction made whether the service is paid for by the subject or their insurance (Standard of Care) or by the study's funding mechanism (Research Sponsored). 2. This generally includes new services or orders placed in EPIC for research subjects.

If answered, "yes", this study will need to be set up in OnCore, Yale's clinical research management system, for Epic to appropriately route research related charges. Please contact [contact]

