Research Plan: We plan to conduct a randomized, single-blind intervention trial to test the comparative effectiveness of an EHR BPA system that informs practitioners (physicians, NPs, and PAs) about what medications they can prescribe that are evidence based and FDA approved for HFrEF versus usual care (no alert and how things are done currently). This will be done across outpatient internal medicine and cardiology clinics of the four teaching hospitals within the Yale New Haven Health System, including Yale New Haven Hospital, St. Raphael's Campus, Greenwich Hospital, and Bridgeport Hospital.

Study Population: One hundred outpatient cardiology and internal medicine providers (to include physicians, NPs, and PAs) practicing at either Yale New Haven Hospital, St. Raphael's Campus, Greenwich Hospital, or Bridgeport Hospital will be enrolled and undergo randomization to either an intervention (alert) group or a control (usual care) group. Those in the intervention group will receive an informational alert for their eligible adult outpatients. Those in the control group will not receive any alerts and will continue to care for patients as usual.

Adult outpatients of randomized providers within internal medicine and cardiology clinics at one of the eligible study sites who have HFrEF with a left ventricular ejection fraction of less than or equal to 40% and are registered in the Yale Heart Failure Registry (NCT04237701) will be automatically enrolled into the study. Patient subjects will either be placed into the alert or usual care group based on the randomization status of their provider at the time of the clinic visit in which they meet eligibility criteria.

Our study flow is the following:

Subject Recruitment

One hundred outpatient providers (to include physicians, PAs, and NPs) of Cardiology and Internal Medicine at the four teaching hospitals within the Yale health system will be selected for potential participation in the study. Providers will be selected based on the frequency with which they see patients who meet the inclusion criteria (see below), as identified by retrospective review of outpatient clinical encounters within Epic. Upon identification, all providers will be approached for consent to participate in the study.

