Eligible patient subjects will be identified through our best practice alert build within Epic using similar methodology that has been used in other ongoing studies by the PIs. Upon opening the patient's medical chart and placing orders, the build will examine the patient record, and all patients who meet inclusion and exclusion criteria will automatically be identified and enrolled into the study. The inclusion criteria will be all adults ≥ 18 years who are seen in an internal medicine or cardiology clinic of one of our study sites and who have a left ventricular ejection fraction of $\leq 40\%$ and membership in the Yale Heart Failure Registry (NCT04237701). Our target sample size is 655 subjects per study arm, for a total of 1310 patients. A patient's study arm (whether a patient generates an alert or not) will be determined by the randomization status of the provider at the time of their first eligible outpatient visit.

As this is an intervention assessing the influence of an alert system on provider behaviors surrounding heart failure prognosis, we cannot inform patients of their participation in the study at the time of enrollment, as this would contaminate the randomized exposure. As this study presents minimal risk to patients, we will be requesting a waiver of informed consent at the patient level.

Randomization

Randomization in this study will occur at the level of the provider. All consented physicians will be randomized within Epic to either the intervention group or the control (usual care) group via a permuted block randomization scheme to ensure an equal number of providers in each study arm. Logic checks within the alerts ensure that once a provider is assigned to an arm, they remain in that arm for the remainder of the study. This will create 100 clusters (providers) to which eligible patient participants will be assigned upon their outpatient visit.

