Should a patient have a documented allergy or contraindication to a particular medication class, this class will not be displayed in the order set for that patient. We will also provide the clinician with the opportunity to dismiss the alert and indicate the reason, including if the patient had any contraindications. Any patient seen by a provider that is randomized to the control study arm will not generate an alert for their provider, but a "silent alert" that registers the patient into the study. Patients will receive care as usual.

Endpoints: The primary outcome for the trial will be the proportion of patients with HfrEF who have an increase in the number of prescribed evidence-based therapies for HfrEF (beta-blockers, ACE-I/ARB/ARNI, MRA, SGLT2i) 30 days post randomization. This endpoint will be based on the prescription of medication rather than filling of the prescription by the patient.

Secondary outcomes will include: percentage of patients prescribed each medication class (i.e. percentage on beta-blockers, percentage on ACE-I/ARB/ARNIs, percentage on SGLT2i, and percentage on MRAs), the percent of filled prescriptions (as assessed by Sure Scripts), medication doses, one-year all-cause mortality, 30-day all-cause hospital admission rate, all-cause 30-day ED visits, and 6 month total healthcare costs. Other data that is present in the EHR that might be related to adverse events such as falls will also be collected. Outcomes will be determined by review of medical, hospital, and billing records.

Secondary analyses will look at outcomes based on insurance coverage, specialty of the provider, and according to prescriptions filled by patients. We will also stratify analyses by provider type (MD vs PA vs NP). Finally, per request of our DSMB, we will collect laboratory values and vital signs as categorical variables to enable simpler detection of safety signals as the data accrues, as well as secondary endpoints at 60 days (to include ED visits, hospitalizations, and all-cause mortality).

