The primary outcome is the percentage of HFrEF patients on a higher number of evidence-based therapies at 30-days after randomization. Our preliminary data suggests that the baseline rate for increasing evidence-based therapy use after a visit is up to 20%. A clinically meaningful increase from that baseline would be 10%. In a fixed design with no interim analysis, sample sizes of 650 in group 1 and 650 in group 2, which were obtained by sampling 50 clusters with 13 subjects each in group 1 and 50 clusters with 13 subjects each in group 2, achieve 91.207% power to detect a difference between the group proportions of 0.1. After accounting for the 2 interim analyses, the final sample size is 1310. The proportion in group 1 (the treatment group) is assumed to be 0.2 under the null hypothesis and 0.3 under the alternative hypothesis. The proportion in group 2 (the control group) is 0.2. The test statistic used is the two-sided Z-Test (Unpooled). The intracluster correlation is a conservative 0.05, and the significance level of the test is 0.048.

Interim Analysis:

We plan to have interim analyses when 25% (n=328), and 50% (n=655) of patients have been enrolled. The interim analyses will allow us to alter the sample size or stop the trial earlier for ethical considerations, unexpected adverse events, or high efficacy. Earlier stopping will be considered for the reason of safety and efficacy. This is a novel intervention and we are obligated to ensure the safety of the alert and that it is minimal risk. The trial will stop for declaring efficacy if the effect size is large. We will use the O'Brien and Fleming stopping rule to stop the trial earlier if the P value for the primary outcome is 0.00007 for efficacy at 25% enrollment, and 0.005 at 50% enrollment.

Statistical Analysis:

The primary analysis will utilize the intention to treat principle. A generalized linear model will be used to assess the relationship between randomization status and the primary outcome. The model will use a log-link and independent correlation structure to allow for calculation of adjusted risk ratios. Statistical significance will be based on a P value of <0.048 to account for two interim analyses. For categorical secondary outcomes, a similar generalized linear modelling approach will be used. For continuous secondary outcomes, a generalized linear model will be used with an identity-link to describe adjusted absolute differences between outcomes.

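### Providers are randomised in permuted blocks with no stated strata, although specialty and HFrEF volume are known beforehand: an avoidable loss of precision, not a bias

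*Combined protocol and SAP*

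**What the plan says.** **Allocation.** Section I, Randomization, makes the provider the unit and allocates "via a permuted block randomization scheme to ensure an equal number of providers in each study arm". It adds: "This will create 100 clusters (providers) to which eligible patient participants will be assigned upon their outpatient visit". Neither a stratification factor nor a block size is given. Matching, minimisation and covariate constraints do not appear anywhere in the document.

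**What is known beforehand.** Section I, Subject Recruitment, draws on "One hundred outpatient providers (to include physicians, PAs, and NPs) of Cardiology and Internal Medicine at the four teaching hospitals". It also states: "Providers will be selected based on the frequency with which they see patients who meet the inclusion criteria". That frequency comes from a retrospective review of Epic encounters. Specialty and past volume are therefore on file for each provider before allocation.

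**Analysis.** Section I, Endpoints, announces: "Secondary analyses will look at outcomes based on insurance coverage, specialty of the provider". The Statistical Analysis section fits a log-link model with an independence working structure and promises adjusted risk ratios, but names no adjustment variable.

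**Power.** Sample Size Determination assumes "50 clusters with 13 subjects each in group 1 and 50 clusters with 13 subjects each in group 2", rates of 0.2 and 0.3, an ICC of 0.05 and a significance level of 0.048, and reports 91.207% power.

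**The concern.** Equal numbers of providers do not give equal case mix. Two specialties sit in one list, and providers are likely to differ in how many HFrEF patients they see. Under an independence structure each patient counts equally, so a high-volume provider weighs more. What matters is the balance of patients, and the blocks do not address it.

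With only 100 randomised units, the arms can differ by chance in the share of patients treated in cardiology. If prescribing changes differ by specialty, that gap adds noise to the primary contrast. The noise could have been removed at almost no cost, because both factors are already in hand. It also leaves the result open to the comment that one arm simply had more cardiology patients. No analysis step makes up for it, since no covariate is named.

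**Working it through.** **1. The plan's own power figure.** Inputs are from Sample Size Determination.
- Design effect: 1 + (13 - 1) x 0.05 = 1.6.
- SE of the risk difference: sqrt[(0.2 x 0.8 + 0.3 x 0.7) x 1.6 / 650] = sqrt(0.37 x 1.6 / 650) = 0.0302.
- Power at two-sided 0.048: Phi(0.1/0.0302 - 1.977) = 90.9%. At two-sided 0.05 the result is 91.207%, exactly the stated figure. The text pairs that figure with 0.048, a small mismatch that does not affect this point.

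**2. Balance in provider counts.** Without strata, the number of cardiology providers in one arm is approximately hypergeometric (100 providers, K in cardiology, 50 drawn). The documents do not give K. The SD of the arm difference in cardiology share is 10.1 points at K = 50, 9.2 at K = 30 or 70, and 8.0 at K = 20 or 80. A gap of 20 points or more has probability 7.1%, 4.9% and 2.3% respectively.

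**3. Balance in patients.** This was simulated with 100 providers and 1310 patients. Volumes were lognormal with the stated CV within specialty, doubled for cardiology, and blocks were of 4. The volume stratum was above or below the specialty median. Cells show the percentage of allocations in which the patient-level cardiology share differs between arms by at least 10 points.

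| Cardiology providers | CV 0.4, no strata | CV 0.4, specialty x volume | CV 0.8, no strata | CV 0.8, specialty x volume |
|---|---|---|---|---|
| 20% | 41 | 4 | 48 | 19 |
| 30% | 39 | 1 | 48 | 16 |
| 50% | 30 | 0 | 38 | 8 |
| 70% | 15 | 0 | 22 | 2 |
| 80% | 6 | 0 | 11 | 1 |

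Specialty strata alone give 16% at 50% cardiology and CV 0.8. The sizes move a great deal with the assumptions, but specialty x volume strata are better than no strata in every row.

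**4. What this is worth in power.** Suppose half the providers are in cardiology and the specialties differ by D in the primary outcome.
- Between-specialty variance: 0.25 x D^2.
- Total between-provider variance implied by the ICC: 0.05 x 0.2 x 0.8 = 0.008.
- Residual ICC once specialty is in the model: (0.008 - 0.25 x D^2) / 0.16.

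| Assumed D | Residual ICC | Design effect | Power at 0.048 |
|---|---|---|---|
| none | 0.050 | 1.600 | 90.9% |
| 5 points | 0.046 | 1.553 | 91.7% |
| 10 points | 0.034 | 1.413 | 93.9% |
| 15 points | 0.015 | 1.178 | 97.0% |

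Taking the outcome variance at the average rate instead (0.25 x 0.75 = 0.1875) gives 91.6%, 93.5% and 96.3%. An uneven split gains less. At 20% or 80% cardiology and D = 10 points, the between-specialty variance is 0.2 x 0.8 x 0.01 = 0.0016, the residual ICC is 0.04, the design effect is 1.48, and power is 92.9%.

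**5. Shift in a single trial.** With D = 10 points, a 20-point imbalance moves the risk difference by 0.20 x 0.10 = 2 points. The target is 10 points and the SE is 3.0. At 50% cardiology and CV 0.8, such a gap arises in about 8% of unstratified allocations.

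**The case against.** The strongest reply is that this variance is already paid for. The ICC of 0.05 covers all differences between providers, including specialty, so the 2-point shift lies inside the planned SE of 3.0 and is not added to it. The design is above 90% power without strata, and unstratified blocks with 100 clusters are defensible. All of that stands, and it limits the point to precision and credibility.

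Three stronger readings are tempting, and the documents do not support them.

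- **Bias.** A reader might infer that a positive or negative result could not be trusted. Randomisation remains valid, and chance imbalance is covered by the cluster-level error, provided the analysis accounts for clustering.
- **Specialty as a strong predictor of prescribing.** No outcome rate by specialty is given, only one baseline of up to 20%. The outcome is an increase in the number of drug classes, and patients already on all four are excluded, so even the direction of a specialty difference is unknown. The 5-15 points used here are assumptions.
- **Badly split provider-type subgroups.** The plan also analyses by MD, PA and NP. A group of 15 providers would split 2:1 or worse in about 26% of unstratified allocations. Under specialty x volume strata the figure is still about 26%, because those strata do not balance provider type. It is no argument for this change.

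Two further replies have weight. Naming covariates in the promised adjusted model would recover much of the loss without touching allocation. And allocation may already have happened: the current text records a data monitoring request about accruing data, and the alert logic locks each provider's arm. The documents do not say whether providers have been randomised.

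**Conclusion.** The point holds as a cheap, modest improvement. The plan states no strata, both candidate factors are known before allocation, one of them defines a planned analysis, and no covariate is named to compensate.

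The size depends on facts the documents do not give. Across the assumed ranges, a patient-level gap of at least 10 points in cardiology share falls from about 6-48% of allocations to about 0-19%. The power gain is at most about 1 point if specialties differ by 5 points, about 3 at 10 and about 6 at 15. It depends on having specialty in the model as well as in the allocation. If the specialties do not differ in outcome, there is no gain in power and only the appearance of balance improves.

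**What to change.** **If providers are not yet allocated:** run the same permuted blocks within four strata, specialty (cardiology / internal medicine) x retrospective HFrEF volume (above / below the specialty median). State the block size in a document that recruiting staff do not see. Name both factors as covariates in the primary model.

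**If providers are already allocated:** leave the allocation alone. Before unblinding, prespecify specialty and baseline volume as the covariates behind the adjusted risk ratios, and report the balance of patients by specialty and arm.

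**Cost:** four lists in Epic instead of one, a few incomplete blocks, and no extra patients. Strata hold about 25 providers each if the specialties are even. At a 20:80 split the smaller specialty has only about 10 per stratum, so small blocks are needed. In the simulation with a volume CV of 0.4, the volume stratum then added nothing over specialty alone (a gap of at least 10 points in about 4% against about 3%), so the actual provider counts should be checked before fixing the strata.
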